6. DOSE MODIFICATIONS

If toxicity occurs, the toxicity will be graded utilizing the NCI CTCAE v4.03 (https://evs.nci.nih.gov/ftp1/CTCAE/CTCAE_4.03/CTCAE_4.03_2010-06-14_QuickReference_8.5x11.pdf), and appropriate supportive care treatment will be administered to decrease the signs and symptoms thereof.

There will be no dose reduction of nivolumab; however, treatment delays are allowed. If the toxicity does not resolve to NCI CTCAE \leq Grade 1 after 28 days, then the patient should be withdrawn from the study and observed until resolution of the toxicity.

The dose modifications to be used in this study are presented in Table 1.

CONFIDENTIAL

STUDY DRUG: NIVOLUMAB

SARAH CANNON DEVELOPMENT INNOVATIONS STUDY NUMBER:

FINAL PROTOCOL DATE: 07 FEB 2020

BMT 24

VERSION 7

Table 1 **Dose Level Modifications**

Adverse Reaction	Severity*	Dose Modification
Colitis	Grade 2 diarrhea or colitis	Withhold dose ^a
	Grade 3 diarrhea or colitis	Withhold dose ^a
	Grade 4 diarrhea or colitis	Permanently discontinue
Pneumonitis	Grade 2	Withhold dose ^a
	Grade 3 or 4	Permanently discontinue
Hepatitis	AST or ALT >3 and up to 5 × the ULN or total bilirubin >1.5 and up to 3 × the ULN	Withhold dose ^a
	AST or ALT >5 × the ULN or total bilirubin > 3 × the ULN	Permanently discontinue
Hypophysitis	Grade 2 or 3	Withhold dose ^a
	Grade 4	Permanently discontinue
Adrenal Insufficiency	Grade 2	Withhold dose ^a
	Grade 3 or 4	Permanently discontinue
Type 1 Diabetes Mellitus	Grade 3 hyperglycemia	Withhold dose ^a
	Grade 4 hyperglycemia	Permanently discontinue
Nephritis and Renal Dysfunction	Serum creatinine >2.5 and up to 6 × the ULN	Withhold dose ^a
	Serum creatinine >6 × the ULN	Permanently discontinue
Rash	Grade 3	Withhold dose ^a
	Grade 4	Permanently discontinue
Encephalitis	New-onset moderate or severe neurologic signs or symptoms	Withhold dose ^a
	Immune-mediated encephalitis	Permanently discontinue
Other	Other Grade 3 adverse reaction First occurrence	Withhold dose ^a
	Recurrence of same Grade 3 adverse reactions	Permanently discontinue
	Life-threatening or Grade 4 adverse reaction	Permanently discontinue
	Requirement for 10 mg per day or greater prednisone or equivalent for more than 12 weeks	Permanently discontinue
	Persistent Grade 2 or 3 adverse reactions lasting 12 weeks or longer	Permanently discontinue

*Toxicity was graded per NCI CTCAE v. 4.03.

^a Resume treatment when adverse reaction returns to Grade 0 or 1.

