 - Left ventricular ejection fraction (LVEF) <45% as determined by multiple gated acquisition (MUGA) scan or echocardiogram (ECHO)
 - Corrected QT (QTc) interval >480 ms on screening electrocardiogram (ECG)
 - Unstable angina pectoris
 - Congestive heart failure (New York Heart Association (NYHA) \geq Grade 2 [Appendix B])
 - Acute myocardial infarction
 - Conduction abnormality not controlled with pacemaker or medication
 - Significant ventricular or supraventricular arrhythmias (patients with chronic rate-controlled atrial fibrillation in the absence of other cardiac abnormalities are eligible)
 - Valvular disease with significant compromise in cardiac function
14. Inadequately controlled hypertension (i.e., systolic blood pressure [SBP] >180 mmHg or diastolic blood pressure [DBP] >100 mmHg) (patients with values above these levels must have their blood pressure [BP] controlled with medication prior to starting treatment).
15. Serious active infection at the time of treatment, or another serious underlying medical condition that would impair the ability of the patient to receive protocol treatment.
16. Known diagnosis of human immunodeficiency virus, hepatitis B, or hepatitis C. Testing at baseline is not required.
17. Presence of other active cancers, or history of treatment for invasive cancer \leq 5 years. Patients with Stage I cancer who have received definitive local treatment and are considered unlikely to recur are eligible. All patients with previously treated in situ carcinoma (i.e., non-invasive) are eligible, as are patients with history of non-melanoma skin cancer.
18. Psychological, familial, sociological, or geographical conditions that do not permit compliance with the protocol.

CONFIDENTIAL

STUDY DRUG: NIVOLUMAB

SARAH CANNON DEVELOPMENT INNOVATIONS STUDY NUMBER:

FINAL PROTOCOL DATE: 07 FEB 2020

BMT 24

VERSION 7

3.3 **Discontinuation from Study Treatment**

Patients will be discontinued from study treatment for any of the following reasons:

- Disease progression
- Irreversible or intolerable toxicity or abnormal laboratory values thought to be related to drug toxicity
- Conditions requiring therapeutic intervention not permitted by the protocol
- Intercurrent illness (this will be at the Investigator's discretion)
- Inability of the patient to comply with study requirements
- Patient requests to discontinue treatment
- Patient withdraws consent from the study
- Non-compliance/lost to follow-up
- Pregnancy

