5. STUDY DESIGN

This is a Phase II single-arm open-label study of nivolumab as maintenance therapy after autologous stem cell transplantation in patients with HL at risk of relapse or progression.

Patients will receive nivolumab (240 mg IV) every 2 weeks (± 2 days as long as interval between doses is 12-16 days) starting 45-180 days post-transplant for up to a maximum of 6 months of treatment. To compare immune recovery, a control group of 5 patients will receive standard-of-care procedures and treatment both pre- and post-transplant. Response to treatment for patients receiving study drug will be assessed 6 months and 1 year post-transplant using the Recommendations for Initial Evaluation, Staging, and Response Assessment of Hodgkin and Non-Hodgkin Lymphoma: The Lugano Classification (Cheson et al. 2014, see Appendix F).

The planned enrollment for this study is 40 patients: 35 patients receiving study drug and 5 patients will receive standard-of-care procedures and treatment both pre- and post-transplant.

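### Section 6 withdraws a patient for toxicity unresolved after 28 days, while Table 1 restarts withheld doses with no time limit and stops persistent Grade 2 or 3 reactions at 12 weeks; no readable passage says which governs

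*Combined protocol and SAP*

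**What the plan says.** The Section 6 text first states: "There will be no dose reduction of nivolumab; however, treatment delays are allowed". It then sets a limit that is not confined to any particular reaction: a patient whose toxicity has not reached Grade 1 or lower is dealt with as follows, "after 28 days, then the patient should be withdrawn from the study and observed until resolution of the toxicity". The day on which the 28 days begin is not given.

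The next sentence hands over to the table: "The dose modifications to be used in this study are presented in Table 1". In Table 1, every row that withholds the dose carries footnote a: "Resume treatment when adverse reaction returns to Grade 0 or 1". The footnote has a grade condition and no time condition. The last block of the table withholds the dose for "Other Grade 3 adverse reaction First occurrence" and, a few rows further down, permanently discontinues for "Persistent Grade 2 or 3 adverse reactions lasting 12 weeks or longer". A neighbouring row permanently discontinues when prednisone at 10 mg per day or more (or equivalent) is needed for more than 12 weeks.

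**The concern.** One section gives a 28-day limit in its text and a 12-week limit in its table, and the sentence between them does not say whether the table replaces the text or is subject to it. Two sites, each following a passage of the same section, could handle the same patient differently.

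This bears on the main purpose of the trial. Safety and tolerability is the primary objective (Section 2.1), and adverse events that lead to discontinuation are a listed safety endpoint (Section 2.4.1). For a reaction that resolves late, both the patient's handling and the count in that endpoint can depend on which passage a site follows.

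**Working it through.** The protocol states no figure to reproduce here. The check is a comparison of the rules, followed by short arithmetic.

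**Inputs.** 28 days (Section 6 text); 12 weeks (Table 1, last block); dosing every 2 weeks, "as long as interval between doses is 12-16 days" (Section 5); 35 patients planned to receive study drug (Section 5).

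**Step 1: count the rows.** Table 1 has 24 rows, of which 11 withhold the dose and 13 discontinue permanently. The withholding rows are colitis 2, and pneumonitis, hepatitis, hypophysitis, adrenal insufficiency, type 1 diabetes, nephritis, rash, encephalitis and first other Grade 3 reaction 1 each: 2 + 9 = 11 rows in 10 reaction categories.

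**Step 2: try to apply both rules together.** Suppose the 28 days cap every restart under Table 1.

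| Grade 3 entries stated by grade | Action in Table 1 |
|---|---|
| Colitis, hypophysitis, hyperglycemia, rash, first other reaction | Withheld (5) |
| Pneumonitis, adrenal insufficiency, recurrence of the same reaction | Discontinued at once (3) |

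- If the 28-day sentence limits dose delays only, a withheld Grade 3 reaction is already out at 28 days and the other three are out immediately. None can reach the 12-week row, so that row has no effect for Grade 3.
- If the sentence covers any toxicity, as its wording allows, a Grade 2 reaction also leaves at 28 days and the whole 12-week row has no effect.

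Either way, part of Table 1 does nothing.

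**Step 3: follow one patient.** Take a first other Grade 3 reaction that returns to Grade 1 on day 40 from onset. If the 28 days run from onset, the text has already withdrawn this patient (40 > 28). Under Table 1 the dose is withheld, the 12-week row has not been reached (40 < 84), and footnote a lets treatment resume. This case needs no assumption about table layout, because the withholding row and the 12-week row stand in the same block.

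**Step 4: width of the window.**

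- 12 weeks = 12 × 7 = 84 days.
- Both periods from onset: 84 − 28 = 56 days, or 56/14 = 4 dosing intervals.
- Assumption for the other end of the range: the 28 days run from a withheld dose that falls up to 16 days after onset, 16 days being the longest stated dose interval. Then 28 + 16 = 44, and 84 − 44 = 40 days.

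Under the second assumption the day-40 patient is not in dispute, so the missing start day itself matters.

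**Step 5: effect on the endpoint.** One patient among 35 is 1/35 = 2.86%, or 2.9 percentage points.

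**Not affected:** reactions that resolve within 28 days, reactions discontinued at once, and reactions that start with fewer than 28 days of treatment left.

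**The case against.** The strongest reply is that this is silence, not contradiction. Footnote a sets a grade for restarting and does not say that restart is allowed at any time. The text uses the same grade and adds a time limit, so a site can obey both by restarting only within 28 days. While a reaction stays unresolved between day 28 and day 84, neither rule tells anyone to give a withheld dose. Stop rules of different lengths may overlap without harm.

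Part of this stands. The dispute concerns whether the patient is withdrawn at 28 days and whether treatment may restart after late resolution. It does not concern dosing during an unresolved reaction. Table 1 therefore permits a restart only in the sense that nothing in it forbids one. If the 28-day sentence is read as a limit on delays, the 12-week row also keeps a use for Grade 2 reactions that Table 1 does not withhold, such as Grade 2 rash.

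The combined reading still removes the Grade 3 content of a row that names Grade 3 explicitly, and the protocol does not say that this reading is intended. A site that takes the 12-week row at face value is following the table it was told to use.

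Two further limits are fair. Section 6.1 refers management to Appendix G, whose flowcharts are not shown. Its readable text includes a note on delaying rather than discontinuing in a hepatic band, but no precedence rule; a timing rule inside the flowcharts cannot be excluded. Also, adverse events are recorded whichever rule is followed (Section 11.1.5), and their analysis is descriptive with no threshold (Section 10.4.3).

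**Conclusion.** The point holds. Section 6 contains two time rules for unresolved toxicity that cannot both have full effect, and no readable passage ranks them. The disputed window lasts up to 56 days if both periods run from onset, or 40 days under the assumption in the working. Each affected patient moves the discontinuation endpoint by at most 2.9 percentage points, taking 35 treated patients as planned. This is an upper bound: a patient who restarts and later stops for the same event counts under either rule, and the Safety Population is whoever is actually dosed (Section 10.3). The number affected is unknown and may be zero.

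Three stronger inferences are not supported:

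- **A window open to the six-month treatment maximum for the named reactions.** This would require the 12-week row to exclude them. The row sits in the last block, but its wording is general and is not limited to other reactions. The neighbouring 12-week steroid row would in any case close the window for patients who need prolonged steroids.
- **A conflict with Section 3.3.** That section lists "Irreversible or intolerable toxicity or abnormal laboratory values thought to be related to drug toxicity" among general grounds for stopping. The absence of a duration there contradicts neither rule.
- **Loss of follow-up.** The text speaks of leaving the study, whereas Sections 7.4 to 7.6 keep patients who end treatment early in follow-up, including a PET-CT at 1 year post-transplant. The same Section 6 sentence keeps the patient under observation, however, and nothing says that the scan is dropped. This is a minor wording mismatch.

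**What to change.** The sponsor should reconcile the Section 6 text with Table 1, specifically footnote a and the 12-week row, and state:

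- which passage governs when they differ;
- the day from which the 28 days and the 12 weeks are each counted;
- as a minor point, whether a patient who stops for unresolved toxicity leaves treatment or the study, in line with Sections 7.4 to 7.6.

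The Appendix G flowcharts should be checked for consistency with the reconciled wording. This review takes no view on which limit is right.

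The cost is amendment wording and a notice to sites, with no additional patients or procedures.

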6.1 Management of Nivolumab-Related Adverse Events

Management algorithms for the following nivolumab-related AEs are located in Appendix G – gastrointestinal, renal, pulmonary, hepatic, endocrinopathy, skin, and neurological.

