Appendix G: Management Algorithms for Immuno-Oncology Agents

These general guidelines constitute guidance to the Investigator and may be supplemented by discussions with the Medical Monitor representing the Sponsor. The guidance applies to all immuno-oncology agents and regimens.

A general principle is that differential diagnoses should be diligently evaluated according to standard medical practice. Non-inflammatory etiologies should be considered and appropriately treated.

Corticosteroids are a primary therapy for immuno-oncology drug-related AEs. The oral equivalent of the recommended IV doses may be considered for ambulatory patients with low-grade toxicity. The lower bioavailability of oral corticosteroids should be taken into account when switching to the equivalent dose of oral corticosteroids.

Consultation with a medical or surgical specialist, especially prior to an invasive diagnostic or therapeutic procedure, is recommended.

The frequency and severity of the related AEs covered by these algorithms will depend on the immuno-oncology agent or regimen being used.

CONFIDENTIAL

STUDY DRUG: NIVOLUMAB

SARAH CANNON DEVELOPMENT INNOVATIONS STUDY NUMBER:

[figure not shown]
FINAL PROTOCOL DATE: 07 FEB 2020

BMT 24

VERSION 7

GI Adverse Event Management Algorithm

Rule out non-inflammatory causes. If non-inflammatory cause is identified, treat accordingly and continue I-O therapy. Opiates/narcotics may mask symptoms of perforation. Infliximab should not be used in cases of perforation or sepsis.

Patients on IV steroids may be switched to an equivalent dose of oral corticosteroids (e.g. prednisone) at start of tapering or earlier, once sustained clinical improvement is observed. Lower bioavailability of oral corticosteroids should be taken into account when switching to the equivalent dose of oral corticosteroids.

STUDY DRUG: NIVOLUMAB

SARAH CANNON DEVELOPMENT INNOVATIONS STUDY NUMBER:

[figure not shown]
FINAL PROTOCOL DATE: 07 FEB 2020

BMT 24

VERSION 7

Renal Adverse Event Management Algorithm

Rule out non-inflammatory causes. If non-inflammatory cause, treat accordingly and continue I-O therapy

Patients on IV steroids may be switched to an equivalent dose of oral corticosteroids (e.g. prednisone) at start of tapering or earlier, once sustained clinical improvement is observed. Lower bioavailability of oral corticosteroids should be taken into account when switching to the equivalent dose of oral corticosteroids.

CONFIDENTIAL

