[figure not shown]
STUDY DRUG: NIVOLUMAB
 SARAH CANNON DEVELOPMENT INNOVATIONS STUDY NUMBER:
 FINAL PROTOCOL DATE: 07 FEB 2020

BMT 24

VERSION 7

Pulmonary Adverse Event Management Algorithm

Rule out non-inflammatory causes. If non-inflammatory cause, treat accordingly and continue I-O therapy. Evaluate with imaging and pulmonary consultation.

Patients on IV steroids may be switched to an equivalent dose of oral corticosteroids (e.g. prednisone) at start of tapering or earlier, once sustained clinical improvement is observed. Lower bioavailability of oral corticosteroids should be taken into account when switching to the equivalent dose of oral corticosteroids.

STUDY DRUG: NIVOLUMAB

SARAH CANNON DEVELOPMENT INNOVATIONS STUDY NUMBER:

[figure not shown]
FINAL PROTOCOL DATE: 07 FEB 2020

BMT 24

VERSION 7

Hepatic Adverse Event Management Algorithm

Rule out non-inflammatory causes. If non-inflammatory cause, treat accordingly and continue I-O therapy. Consider imaging for obstruction.

Patients on IV steroids may be switched to an equivalent dose of oral corticosteroids (e.g. prednisone) at start of tapering or earlier, once sustained clinical improvement is observed. Lower bioavailability of oral corticosteroids should be taken into account when switching to the equivalent dose of oral corticosteroids.

*I-O therapy may be delayed rather than discontinued if AST/ALT ≤ 8 x ULN or T.bili ≤ 5 x ULN.

**The recommended starting dose for grade 4 hepatitis is 2 mg/kg/day methylprednisolone IV.

STUDY DRUG: NIVOLUMAB

SARAH CANNON DEVELOPMENT INNOVATIONS STUDY NUMBER:

[figure not shown]
FINAL PROTOCOL DATE: 07 FEB 2020

BMT 24

VERSION 7

Endocrinopathy Management Algorithm

[figure not shown]
Rule out non-inflammatory causes. If non-inflammatory cause, treat accordingly and continue I-O therapy. Consider visual field testing, endocrinology consultation, and imaging.

Patients on IV steroids may be switched to an equivalent dose of oral corticosteroids (e.g. prednisone) at start of tapering or earlier, once sustained clinical improvement is observed. Lower bioavailability of oral corticosteroids should be taken into account when switching to the equivalent dose of oral corticosteroids.

Skin Adverse Event Management Algorithm

Rule out non-inflammatory causes. If non-inflammatory cause, treat accordingly and continue I-O therapy.

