Patients on IV steroids may be switched to an equivalent dose of oral corticosteroids (e.g. prednisone) at start of tapering or earlier, once sustained clinical improvement is observed. Lower bioavailability of oral corticosteroids should be taken into account when switching to the equivalent dose of oral corticosteroids.

*Refer to NCI CTCAE v4 for term-specific grading criteria.

^If SJS/TEN is suspected, withhold I-O therapy and refer patient for specialized care for assessment and treatment. If SJS or TEN is diagnosed, permanently discontinue I-O therapy.

CONFIDENTIAL

STUDY DRUG: NIVOLUMAB

SARAH CANNON DEVELOPMENT INNOVATIONS STUDY NUMBER:

[figure not shown]
FINAL PROTOCOL DATE: 07 FEB 2020

BMT 24

VERSION 7

Neurological Adverse Event Management Algorithm

Rule out non-inflammatory causes. If non-inflammatory cause, treat accordingly and continue I-O therapy.

Patients on IV steroids may be switched to an equivalent dose of oral corticosteroids (e.g. prednisone) at start of tapering or earlier, once sustained clinical improvement is observed. Lower bioavailability of oral corticosteroids should be taken into account when switching to the equivalent dose of oral corticosteroids.

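### The Appendix G hepatic footnote permits delay at liver-test levels where Table 1 requires nivolumab to be stopped for good, and no sentence ranks the two

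*Combined protocol and SAP*

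**What the plan says.** The hepatitis rows of Table 1 (Section 6) have two steps. Nivolumab is withheld for AST or ALT above 3 and up to 5 × ULN, or total bilirubin above 1.5 and up to 3 × ULN. It is permanently discontinued for "AST or ALT >5 × the ULN or total bilirubin > 3 × the ULN". The table's note on resuming once the reaction is Grade 0 or 1 is attached to the withhold rows only.

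The hepatic page of Appendix G carries a footnote: "I-O therapy may be delayed rather than discontinued if AST/ALT ≤ 8 x ULN or T.bili ≤ 5 x ULN".

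Three statements bear on which text rules:

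- Section 6: "The dose modifications to be used in this study are presented in Table 1".
- Appendix G, introduction: "These general guidelines constitute guidance to the Investigator", and "The guidance applies to all immuno-oncology agents and regimens".
- Section 6.1: "Management algorithms for the following nivolumab-related AEs are located in Appendix G", with hepatic events among those named. Section 8.1.3 also refers to Appendix G for managing nivolumab-related events.

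Section 6 allows treatment delays, with a limit: if a toxicity has not come down to at most "Grade 1 after 28 days, then the patient should be withdrawn from the study". Safety and tolerability are the primary objective (Section 2.1). AEs leading to discontinuation are a safety endpoint (Section 2.4.1) and a planned summary (Section 10.4.3).

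**The concern.** Two numerical rules for the same laboratory finding sit in one protocol, and the more lenient one is on the page a clinician would open when managing a liver event. That page gives a specific permission to delay, and the visible text has no pointer back to Table 1. Section 6.1, which sends the reader there, is itself part of the dose-modification section.

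Two things are at stake. One is re-exposure: Table 1 rules out further nivolumab after liver-test elevations of this size, and the footnote leaves it open. The other is counting. The study has six sites, so the same laboratory result could be recorded as a discontinuation at one and as a dose delay at another, and the summary of events leading to discontinuation would then partly reflect which page a site had followed.

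**Working it through.** The protocol states no figure to reproduce here, so the check compares intervals and then looks for a precedence rule.

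**Step 1. The two rules side by side** (Table 1 against the Appendix G footnote, in multiples of ULN)

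| Liver test | Table 1 | Footnote |
|---|---|---|
| AST/ALT >3 to 5 | withhold | delay allowed; no conflict |
| AST/ALT >5 to 8 | stop permanently | delay allowed; **conflict** |
| Bilirubin >1.5 to 3 | withhold | delay allowed; no conflict |
| Bilirubin >3 to 5 | stop permanently | delay allowed; **conflict** |

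Read narrowly, with both footnote limits required to hold, the conflict region is:

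(AST/ALT >5 or bilirubin >3) and (AST/ALT ≤8 and bilirubin ≤5).

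Where AST/ALT is at most 5 and bilirubin at most 3, Table 1 asks for no more than withholding. The footnote therefore changes a Table 1 action only where Table 1 says stop. It cannot be read as a harmless supplement.

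**Step 2. Is there a precedence rule?** Section 6 names Table 1 as the source of the study's dose modifications. Appendix G calls itself general guidance, and its footnote is permissive. Together these imply that Table 1 governs. Sections 6.1 and 8.1.3 refer to Appendix G without ranking it, and no sentence says what to do when the two differ. A site that stops complies with both texts; a site that delays breaches Table 1.

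**Step 3. Does the 28-day rule close the gap?** Take a patient with AST at 6 × ULN and normal bilirubin who is back to Grade 1 on day 20 (an illustration, not data).

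- Table 1: 6 > 5, so nivolumab is stopped permanently.
- Footnote: 6 ≤ 8, so delay is allowed.
- 28-day rule: 20 < 28, so withdrawal is not triggered.

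Only Table 1 prevents re-dosing. The 28-day rule catches patients who recover slowly or not at all, and misses this one.

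**Step 4. Can affected patients be found?** Yes. The metabolic panel on Day 1 of each cycle includes AST, ALT and total bilirubin (Section 7.3.1 and Appendix E). Section 11.3.3 makes a laboratory result reportable as an AE if it requires a change to, or a stop of, study drug. Section 11.1.5 requires the action taken to be recorded.

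**The case against.** The strongest reply is that the protocol already answers the question. Table 1 is study-specific and mandatory; Appendix G is generic and optional. The cross-references speak of managing adverse events, while Section 6 gives dose modification to Table 1. If delaying is plainly a breach, a governing rule exists and only a cross-reference is missing.

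Much of this stands. A reader might infer that the protocol has no governing rule, or that a site may choose between the texts. The documents do not support that: the wording of Section 6 and of the Appendix G introduction points to Table 1. But an implied ranking does not cancel an explicit numerical permission on a page to which the protocol sends its sites. Nor is the split between management and dosing clean, because the Appendix G footnotes themselves speak of delaying, withholding and stopping therapy.

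A reader might also take the footnote's *or* literally, so that a patient with AST at 10 × ULN and bilirubin at 1 × ULN qualifies for delay through the bilirubin limit. That cannot be sustained. The algorithm diagram is not reproduced in the available text, and the box to which the footnote belongs may restrict it. Only the narrow band is supported.

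Finally, the consequence is bounded. Safety is summarised descriptively, no interim analysis is planned (Section 10.5.2), and the 28-day rule limits long delays. All of that stands and holds the severity down.

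**Conclusion.** The conflict is real and confined to AST/ALT above 5 and up to 8 × ULN, or bilirubin above 3 and up to 5 × ULN. In that band the footnote permits a delay that Table 1 forbids, and a patient who recovers within 28 days could be given nivolumab again. The effect is on patient safety and on consistent counting of AEs leading to discontinuation. Severity is minor to moderate.

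Its practical size is unknown, because the documents give no frequency for such patients. With 35 patients planned to receive nivolumab (Section 5), each one delayed rather than stopped lowers the discontinuation proportion by at most 1/35 = 2.9 percentage points. That arithmetic fits any per-patient discrepancy and does not measure this one. A reader might infer that patients have been mismanaged or that the tolerability result is biased; nothing in the documents shows either. No decision rule, sample size or power figure is affected.

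The conclusion rests on the footnote's wording. It assumes that the unseen diagram does not itself restore the Table 1 limits. Any condition for resuming treatment in that diagram cannot be checked.

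**What to change.** Delete the hepatic footnote in Appendix G, or rewrite it so that it offers no delay above AST/ALT 5 × ULN or bilirubin 3 × ULN. Tell sites by memo. List any patient already treated whose values fell in the band, with the action taken.

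Keep the edit to the hepatic page. A blanket sentence that the stricter action always applies would reach all seven organ algorithms named in Section 6.1, whose diagrams are not visible here, and could change other stopping rules unseen. A blanket sentence that Table 1 always prevails has its own drawback: Appendix G says "If SJS or TEN is diagnosed, permanently discontinue I-O therapy", and Table 1 does not name those conditions, although it does stop treatment for Grade 4 rash and for life-threatening reactions.

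The cost is one edited footnote, one memo and one short listing from data already collected. No patients or procedures are added.
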